15.2.1.4. Proportion of Seizure-Free Subjects

Subjects who did not have any seizure as per the paper seizure diary for the intervals of interest will be deemed seizure free, for the corresponding interval of interest. Subjects must complete each interval of interest without any seizures to be considered seizure-free for each interval of interest. Subject with no seizure data available during interval of interest will not be considered seizure-free for the interval of interest. However, subjects who discontinue prior to Visit 9 will be considered not seizure-free for the interval when the discontinuation takes place and all subsequent intervals (even if the subjects are seizure-free at the time of discontinuation). Anyone who drops out from the study and does not complete the 24 weeks (Visit 9), is included in the denominator for the proportion.

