11.2.2.4. Seizure Diaries

To record seizures during the study, a standardized paper seizure diary and an electronic seizure diary will be dispensed at Visit 1. The subjects will be trained on use of the diaries by the site

personnel. The subjects will also receive a copy of the description of seizure types as presented in the DISCOVER form to ensure that the subject will use correct and consistent terminology to describe the seizures they are experiencing during the study.

The diaries will be completed daily throughout the study, up until the end of the Maintenance Phase (Visit 9, EOS). The diaries require an entry on every day whether a seizure occurs or not. Subjects will record information for each seizure in the paper diary and electronic diary at the same time by date and type of seizure. At each return study visit, the seizure diaries will be reviewed by site staff.

Efficacy evaluations of seizures during the study will be based on the information recorded in the standardized paper daily seizure diary.

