7.2. Handling of Dropouts or Missing data

Subjects who dropped out before study completion are not to be replaced and all available information obtained from them will be included in the appropriate efficacy and safety summaries to the time of dropout. No imputation is planned for any safety measures.

If the date of the seizure is missing or incomplete and the seizure cannot be allocated to a study interval, these data will not be used in the analysis, but will be presented in the subject data listings. If the seizure diary was returned and there was no seizure data available for a day during that evaluation period, it will be assumed that the patient had missing seizure data, and the day will be excluded from the calculation of the standardized seizure frequency.

Seizure related variables will be calculated based on available data. For dropout subjects, their seizure frequency will be derived for each interval up to the last interval where the subject had data. The last interval standardized seizure frequency (SSF) will be computed based on available data prior to dropout.

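### Among subjects who complete an interval, a sparse paper diary with no recorded seizure counts as seizure-free, because SAP 15.2.1.4 sets no minimum diary coverage

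*SAP*

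**What the plan says.** SAP 15.2.1.4 starts from the diary: "Subjects who did not have any seizure as per the paper seizure diary for the intervals of interest will be deemed seizure free". It then adds three conditions.

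- Completion: "Subjects must complete each interval of interest without any seizures to be considered seizure-free for each interval of interest". The section does not say whether this refers to visits or to diary days.
- Absence of data: "Subject with no seizure data available during interval of interest will not be considered seizure-free for the interval of interest".
- Dropout: "subjects who discontinue prior to Visit 9 will be considered not seizure-free for the interval when the discontinuation takes place and all subsequent intervals". A subject who "does not complete the 24 weeks (Visit 9), is included in the denominator for the proportion".

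The rule for single blank days is in SAP 7.2 (and in Protocol 15.3.10). If a diary was returned without data for a day, "it will be assumed that the patient had missing seizure data, and the day will be excluded" from the standardized seizure frequency (SSF). That exclusion is written for SSF only. The same section leaves out of the analysis any seizure that cannot be dated to an interval.

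Protocol 11.2.2.4 sets the conduct standard: "The diaries require an entry on every day whether a seizure occurs or not". Neither document sets a minimum number or share of diary days for seizure freedom or for entry to the mITT population. SAP 10 does not name incomplete diaries among the important protocol deviations, though its list is not exhaustive.

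**The concern.** The SAP treats unobserved time in three ways. After dropout it counts as failure. In SSF a blank day is removed. For seizure freedom, a completer's blank day has the same effect as a day observed without a seizure, as long as some entry exists in the interval.

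Seizure freedom over the first 12, last 12 and all 24 maintenance weeks is a listed efficacy endpoint. The study is open-label and makes no comparison between arms, so the rate will be read as an absolute figure with no comparator to offset a classification error. The per-protocol analysis does not clearly remove sparse diaries either.

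**Working it through.** **1. Which reading of completion applies.** If completing an interval meant a full diary, the sentence excluding subjects with no data would be redundant. The last sentence of SAP 15.2.1.4 ties completion of the 24 weeks to Visit 9, and SAP 15.1.1 counts completers by Visit 9/EOS. Staying to the closing visit is therefore the natural reading, although the term is undefined.

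**2. Direction.** The documents state no seizure-free rate or missing-day rate, so there is no plan figure to reproduce. For a completer with no recorded seizure, a blank day can hide a seizure but cannot create one. The classification error is therefore upward or zero.

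**3. Per-subject size (illustration).**

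- Rate: at least 3 seizures in six months (Protocol 8.1, criterion 5). With a half-year taken as 182.5 days, 3 × 28 / 182.5 = 0.46 per 28 days. A second rate of 1 per 28 days is assumed.
- Interval: 24 weeks = 168 days = 6 periods of 28 days.
- Assumptions: no treatment effect, Poisson seizures, diary days missing at random, coverage c varied.
- Formula: P(no recorded seizure) = exp(−rate × 6 × c).

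| Diary coverage c | 0.46 per 28 days | 1 per 28 days |
|---|---|---|
| 100% | exp(−2.76) = 6% | exp(−6) = 0.2% |
| 80% | exp(−2.21) = 11% | exp(−4.8) = 0.8% |
| 50% | exp(−1.38) = 25% | exp(−3) = 5% |
| 25% | exp(−0.69) = 50% | exp(−1.5) = 22% |

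Over 84 days at the lower rate, the chance is 25.1% with a full diary, 35.5% with 25% of days missing and 50.1% with half missing.

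**4. Arm-level size (illustration).** Take an 84-day interval, the lower rate and 60% completion (the Arm 1 assumption in SAP 3.3), with dropouts as failures. Let a share s of completers miss a fraction m of days, and let p(c) be the 84-day probability at coverage c.

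- Full diaries: 0.60 × p(1) = 0.60 × 0.251 = 15.1%.
- Current rule: 0.60 × [(1 − s) × p(1) + s × p(1 − m)].
- Full-diary rule: 0.60 × (1 − s) × p(1).

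| s | m | Full diaries | Current rule | Full-diary rule |
|---|---|---|---|---|
| 10% | 25% | 15.1% | 15.7% | 13.6% |
| 20% | 25% | 15.1% | 16.3% | 12.1% |
| 20% | 50% | 15.1% | 18.1% | 12.1% |
| 30% | 50% | 15.1% | 19.6% | 10.6% |

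The upward error is 0.6 to 4.5 percentage points in these scenarios. With the SAP's approximately 50 subjects per arm, 3 points is 0.03 × 50 = 1.5 subjects. Over 168 days with s = 20%, the full-diary value is 3.8% and the current rule gives 4.5% (m = 25%) or 6.0% (m = 50%).

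**The case against.** **The rule is not as loose as it may look.** A reader might infer that any subject with some diary data and no recorded seizure is counted as seizure-free. The documents do not support that. The interval must be completed, and anyone who discontinues before Visit 9 fails for that interval and all later ones. The point applies only to subjects who complete the interval.

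**Completion could mean a complete diary.** An entry is required every day, so this reading is possible. It is weaker for the reasons in step 1 of the working. If it was intended, the SAP still has to say so, because the two readings produce different tables.

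**Net overstatement is not shown.** A reader might infer that the reported proportion is too high. Counting every dropout as a failure pulls it down, with only 60% and 50% assumed to complete. This objection stands. The dropout rule does not, however, correct misclassification among completers.

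**Coverage may be good, and blanks may be harmless.** Site staff review the diaries at each return visit. If subjects mainly skip the entry on days without seizures, the error shrinks towards zero. This stands too: the coverage values above have no basis in the documents.

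**A coverage threshold brings its own bias.** In the scenario with 20% of completers missing a quarter of days, the full-diary rule is 3.0 points too low and the current rule 1.2 points too high. This is a good reason not to replace the current rule with a single cut-off, but not a reason against showing both.

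**Stakes are limited.** This is one descriptive secondary endpoint with no testing, and the plan provides listings for the diary analyses.

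**Conclusion.** The point holds for subjects who complete an interval. Among them, only a wholly empty diary blocks seizure-free status, so blank days that SAP 7.2 calls missing work in the subject's favour. The error for these subjects can only be upward: from 6% to 25% over 24 weeks if half the days are missing, at the minimum entry rate with no treatment effect, Poisson seizures and days missing at random.

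The arm-level effect is unknown because the documents give no missing-day rate. It is probably a few percentage points.

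It would also be wrong to infer that sparse diaries are the only gap scored as success. A completer whose one reported seizure cannot be dated could be classed as seizure-free as well, since SAP 7.2 leaves that seizure out. A coverage threshold alone would not catch this.

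This is an inexpensive improvement to the definition. It does not show that the endpoint is unusable.

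**What to change.** In SAP 15.2.1.4:

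1. State that completing an interval means reaching its closing visit.
2. For each post-baseline interval, report the seizure-free proportion under the current rule and again with a pre-specified minimum share of days with a paper-diary entry, for example at least 90% and 100%. Completers below the minimum count as not seizure-free and stay in the denominator. The 90% figure is a judgement, not something the documents imply. Baseline is left out because most of it is retrospective history without diary days.
3. Report the distribution of diary coverage among completers, by arm and interval.
4. State that a reported seizure that cannot be dated to an interval prevents seizure-free status for every interval in which it could have occurred.

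If the entries made are accurate, and undated seizures aside, the current-rule and 100% rows bracket the rate that full diaries from the same completers would give, with dropouts still counted as failures.

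The cost is a few sentences and extra table rows, with no change to trial conduct. The coverage-based rows will exclude some truly seizure-free subjects and so err downward, which is why they belong beside the current rule and not in its place.

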15.2.1.5. Time on ESL

Time on ESL will be calculated from the first dose as indicated in the Study Drug Dispensation source to the last known dose of ESL in the Disposition source. Subjects who were still on ESL at the end of study will be censored at the end of study. Subjects who dropped out of the study

while receiving treatment will be an event at the time of the last dose date. Change in dosage levels during the treatment period will be ignored.

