7.3.4. Rationale for the Endpoints

The primary endpoint, retention in the study throughout the 24-week Maintenance Phase, was selected because both efficacy and tolerability/safety factor into the subject's willingness to complete this phase of the study. Therefore, retention is a good measure of the effectiveness of ESL in clinical practice.

Standard measurements are used for the evaluation of changes in seizure activity, safety and evaluations of quality of life, mood and behavior.

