14. STUDY TERMINATION

The Sponsor reserves the right to discontinue the study at this study center or at multiple centers for safety or administrative reasons at any time while safeguarding that early termination does not compromise subjects' safety or well-being. In particular, a study center that does not recruit at an acceptable rate may be closed. Should the study be terminated and/or the study center closed for whatever reason, all documentation must be returned to the Sponsor or its representative.

If, in the opinion of the Investigator, clinical observations suggest it may be unsafe to continue, the Investigator may terminate part or the entire study after consultation with the Sponsor.

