Appendix 1 shows conventions for presentation of data in outputs.

The templates provided with this SAP describe the presentations for this study and therefore the format and content of the summary tables, figures and listings to be provided by IQVIA Biostatistics.

9. Disposition and Withdrawals

All subjects who provide informed consent will be accounted for in this study.

Subject disposition will be summarized and presented for the number and percentage of subjects, who were screened, screen-failed, entered, completed the study, and discontinued early including reasons for discontinuations such as adverse event, lack of efficacy, withdrawal by subject, withdrawal by investigator, protocol deviation, study terminated by Sponsor, death, pregnancy and Other.

Listing of subject disposition will also be provided.

10. Important protocol deviations

Prior to database lock, important protocol deviations (IPDs) will be identified in a review of all protocol deviations reported. Possible IPDs will include, but may not be limited to, subjects who:

- Did not meet inclusion/exclusion criteria or eligibility was not adequately verified
- Received any disallowed concomitant medication
- Developed withdrawal criteria but were not withdrawn

Individual IPDs will be presented in a data listing. The number and percentage of subjects with IPDs will be summarized by type of deviation as categorized above.

11. Demographic and other Baseline Characteristics

Demographics, including (age, gender, race, and ethnicity where applicable), and other baseline characteristics collected at screening, such as height, weight, body mass index, and disease conditions will be summarized using descriptive statistics. These data will be presented as a listing. Demographic data and other baseline characteristics will be presented for the safety and PP population.

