15.1. Primary Variable

15.1.1. Primary Variable & Derivation(s)

The primary outcome variable is the proportion of subjects completing 24 weeks adjunctive therapy during Maintenance Phase (Visit 9) defined as below.

$$\frac{\text{Number of subjects who completed up to and including the end of the Maintenance Phase (Visit 9/ EOS)}}{\text{Number of subjects in the safety population}} \times 100$$

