15.1.2. Primary Analysis of Primary Outcome Variable

The primary analysis will be performed for the safety population.

The number and proportion (%) of subjects completing the 24 weeks of the Maintenance Phase will be provided along with a 95% confidence interval using the exact method.

It will be also summarized by age group, race group, gender, baseline AEDs and number of baseline AEDs.

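### Time on ESL counts an exit caused by a non-safety sponsor or site closure as a discontinuation event, where censoring would be usual

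*SAP*

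**What the plan says.** **Time on ESL.** SAP 15.2.1.5 has one censoring rule: "Subjects who were still on ESL at the end of study will be censored at the end of study". A subject who drops out "while receiving treatment will be an event at the time of the last dose date". Protocol 15.3.6 has the same two rules, except that it dates the event at dropout. Neither text refers to the reason for leaving. SAP 15.2.2.6 plans a median with 95% CI and Kaplan-Meier plots.

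**End of study.** Protocol Table 4 defines this for each subject as the day of completion per design, at Visit 9.

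**Closure.** Protocol Section 14 lets the sponsor stop the study, at one center or several, for safety or administrative reasons, and adds that "a study center that does not recruit at an acceptable rate may be closed". Protocol Section 13 lists sponsor termination among the reasons for discontinuation. SAP Section 9 tabulates it in a list that ends "protocol deviation, study terminated by Sponsor, death, pregnancy and Other".

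**Primary endpoint.** SAP 15.1.1 divides Visit 9 completers by the "Number of subjects in the safety population", and SAP 15.1.2 reports the result "along with a 95% confidence interval using the exact method". Protocol 7.3.4 justifies retention because "both efficacy and tolerability/safety factor into the subject's willingness to complete this phase of the study".

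**The concern.** A Kaplan-Meier analysis of time on drug is meant to describe how long subjects stay on ESL. When follow-up ends because a center is closed for slow recruitment, the subject's own stopping time has not been observed, and the usual treatment is censoring. Under the written rule that subject is an event.

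Two things follow. A decision unrelated to the drug pulls the curve down. Also, since every exit on treatment is an event and censoring happens only at Visit 9, the curve at the end of Maintenance essentially repeats the crude retention proportion. The method's ability to handle incomplete follow-up goes unused. The missing-data sections (Protocol 15.3.10, SAP 7.2) and the analysis sections (SAP 15.1.2, 15.2.2.6) contain no alternative rule or sensitivity analysis for sponsor-initiated exits.

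**Working it through.** **1. The plan's own precision figures.** With n = 1.96² × p(1 − p) / 0.10², p = 0.60 gives 92.2, so 93, and p = 0.50 gives 96.04, so 97. Both match Protocol 15.1. At the SAP's 50 per arm, 1.96 × √(p(1 − p)/50) is 13.6 points at 60% and 13.9 points at 50%. SAP 3.3 states about 14%; it calls this the width, but the figure matches the half-width.

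**2. Which rule catches a closed-out subject.** The subject has not reached Visit 9, so under Table 4 has not reached end of study and does not meet the censoring rule. The subject left while on treatment, so the event rule applies. The same subject stays in the retention denominator and cannot enter the numerator.

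**3. Effect of one exit at 50 per arm.**
- If the subject would certainly have completed: 1/50 = 2 points. This is the upper bound.
- If the chance of completing was the arm's assumed rate: 0.60/50 = 1.2 points (Arm 1), 0.50/50 = 1.0 point (Arm 2).
- A subject closed out late has already survived most of the period, so the effect moves from the lower value towards 2.

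**4. Example for Arm 1 (the counts are assumptions).** Without closures, 30/50 = 60% (exact 95% CI 45.2 to 73.6). Three exits among certain completers (3 × 2 points), or five exits at 1.2 points each, give 27/50 = 54% (39.3 to 68.2). The 6-point shift compares with a half-width of about 14.

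**5. Effect on the curve.** Kaplan-Meier estimates were run on 200,000 simulated subjects. Discontinuation was exponential, set so that the stated share is still on drug at 182 days (26 weeks: 2 of titration plus 24 of Maintenance). An assumed share *a* of subjects was given a closure date, uniform over 182 days.

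| Underlying proportion | *a* | On ESL at 182 days: closure as event | Closure censored | Median: closure as event | Closure censored |
|---|---|---|---|---|---|
| 60% | 5% | 57.0% | 60.1% | not reached | not reached |
| 60% | 10% | 54.0% | 60.0% | not reached | not reached |
| 60% | 20% | 48.0% | 60.1% | 172 days | not reached |
| 50% | 5% | 47.5% | 50.0% | 170 days | not reached |
| 50% | 10% | 45.0% | 50.0% | 158 days | about 182 days |
| 50% | 20% | 40.0% | 50.0% | 139 days | not reached |

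The event-rule column follows p(1 − *a*), for example 0.60 × 0.90 = 54.0%, and equals the crude completion proportion in each run. Censoring recovers the underlying value because closure was simulated as independent of outcome. Some subjects stop before their closure date: at 60% and *a* = 10%, 7.9% actually leave through closure. The 6.0-point drop is then 6.0/7.9 = 0.76 points per 1% of subjects, or about 1.5 points per exit at 50 per arm, between the limits in step 3.

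At 60% the median is not reached under either rule up to *a* = 10%, so the planned median would not show the difference. The proportion at the end of Maintenance would.

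**The case against.** **The rule may not cover closure.** The text speaks of subjects who dropped out, and sponsor closure is not named. A whole-study stop might be read as end of study. Table 4 goes against that reading, and it cannot cover the closure of a single center. What stands is that the sentence is silent on closure; the event reading is the one the definitions support.

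**All-cause discontinuation is a legitimate definition.** This stands for the primary endpoint. A reader might infer that the retention analysis is wrong because Protocol 7.3.4 speaks of willingness, or that closed-out subjects are labeled failures of ESL. The protocol says only that efficacy and tolerability enter into willingness, and the plan distinguishes completers from non-completers.

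**Such subjects really do stop.** A reader might infer that a closed-out subject carries on with commercial ESL and is wrongly scored as stopping. The documents describe commercial continuation only after completing Maintenance, and taper for early exits (Protocol 7.1, 10.1.2 and 13). The point here does not need that scenario: the stop would be caused by the closure.

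**The trigger may never happen.** Section 14 says a slow center may be closed, not that subjects on treatment there must be withdrawn. The difference between about 190 planned subjects in the protocol and about 100 in the SAP might tempt a reader to expect closures. Enrolling fewer subjects does not remove those already enrolled.

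**The counts will be visible.** SAP Section 9 tabulates and lists exits by reason, so crude retention can be recalculated. That limits the harm, but it does not re-estimate the curve.

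**Blanket censoring would bias the other way.** Section 14 also allows termination for safety. Censoring those exits would be informative and would flatter time on ESL. This stands and narrows the remedy.

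**Conclusion.** The point holds as a minor improvement limited to Time on ESL. As written, an exit caused by an administrative closure is an event with no exception, and no planned analysis shows the curve without it. The conclusion rests on three conditions: that closures occur during treatment, that subjects are withdrawn as a result, and that dropping out includes such exits. The study is descriptive with no tests (SAP 6.1, 6.6), so no decision rule is affected. The documents do not support a criticism of all-cause retention as primary, or any forecast of how many closures there will be.

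**What to change.** - Leave the primary retention analysis unchanged.
- Add one sentence to SAP 15.2.1.5: an exit recorded as terminated by the sponsor is censored at last dose when the closure was for non-safety administrative reasons; safety-driven closures remain events.
- State that site closure is coded under the sponsor-termination reason, so that it does not fall under the residual category.
- The single reason code does not separate safety from administrative closures. Classify each closure from the sponsor's documented reason before database lock.
- Add to SAP 15.2.2.6 the Kaplan-Meier proportion on ESL at the end of Maintenance, with 95% CI, as a supportive estimate. Name the study day at which it is read, since Visit 9 has a window of ±3 days.

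The reason and the last-dose date are already planned to come from the disposition source, so the cost is one sentence, a coding instruction and one extra estimate. The downside is the assumption that administrative exits are unrelated to how the subject was doing. That could fail if, for instance, poorly run centers both recruit slowly and retain subjects badly.
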